7.3 Endpoints

Primary endpoint:

The following endpoints will address the primary objective (concerning Saxenda® only):

BMI and comorbidities:

- Number of patients with Body Mass Index (BMI)≥30 kg/m² (measured less than 6 months before date of first prescription).
- Number of patients with 27 kg/m² ≤BMI<30 kg/m² (measured less than 6 months before date of first prescription) and
 - ≥1 relevant comorbidity registered:
 - Dysglycaemia (T2DM or prediabetes), hypertension, dyslipidaemia, and/or obstructive sleep apnoea.
 - o No relevant comorbidities (described above) registered.
- Number of patients with BMI<27 kg/m² (measured less than 6 months before date of first prescription).
- Number of patients with BMI not measured within 6 months before date of first prescription.

 Protocol
 Date:
 23 November 2015
 Novo Nordisk

 Study ID: NN8022-4241
 Version:
 5.0

 UTN: U1111-1185-3661
 Status:
 Final

 EU PAS No.:
 CONFIDENTIAL
 Page:
 17 of 53

Stopping rule:

- Number of patients with at least 5% weight loss (measured 16-24 weeks after first prescription date) and continuing treatment.
- Number of patients with less than 5% weight loss (measured 16-24 weeks after first prescription date) and continuing treatment.
- Mean weight loss (measured 16-24 weeks after first prescription date) in patients not treated according to stopping rule.

Secondary endpoint:

The following endpoint will be used to address the first secondary objective (concerning Victoza[®] only):

- Number of patients with Victoza[®] prescriptions fulfilling at least one of the following criteria:
 - 1. Dose information of 3.0 mg per day, or
 - 2. Indication of weight management.

The following endpoints will be used to address the second secondary objective (concerning Saxenda® only):

- Adherence to dose escalation according to label:
 - o Number of patients who have reached a dose of 3.0 mg within 4-12 weeks after first prescription date.
- Concomitant medication with of other GLP-1 receptor agonists:
 - Number of Saxenda[®] patients with other GLP-1 receptor agonists prescribed during continued treatment with Saxenda[®] (continued treatment is defined as no gaps between prescriptions of more than 90 days, identified by examining repeat prescription dates).
- Duration of treatment with Saxenda®:
 - o Number of patients with a treatment duration of:

Protocol		Date:	23 November 2015	Novo Nordisk
Study ID: NN8022-4241		Version:	5.0	
UTN: U1111-1185-3661		Status:	Final	

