8.2 Setting

Since the purpose of this study is to investigate real-world, in-market utilisation of liraglutide, patients will be identified based on the prescription rather than on a specific diagnosis. The study will target first-time patients of Saxenda® or Victoza® by identifying a representative sample of physicians who treat diabetic or obese patients for whom Saxenda® or Victoza® can be prescribed. These include general practitioners (GPs), endocrinologists and cardiologists (or other diabetes and obesity specialists) from a variety of settings (e.g., office-based vs. hospital-based, urban vs. rural). Once prescribers of Saxenda® or Victoza® are identified, these will be oversampled to ensure adequate numbers of prescribers (and therefore patients).

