8.7.2 Statistical methods

Details of the data analyses, along with table, listing and figure (TLF) templates, will be fully described in a Statistical Analysis Plan (SAP).

In brief, the descriptive analyses will present Saxenda[®] and Victoza[®] utilisation by indication. Results will be evaluated by site characteristics, including country and geographic region within country, to ascertain any patterns of prescribing by specific indication. The main analysis will be to estimate the proportion of prescriptions outside label among Saxenda[®] or Victoza[®] patients during the entire study period in the countries of interest. The proportion of each of the forms of prescription outside label will be described (see section on prescription outside label). Characteristics of patients prescribed Saxenda[®] or Victoza[®] according to the respective approved SmPCs will also be evaluated.

Analyses on the following will be conducted:

Site characteristics

Descriptive statistics will be provided for the following variables:

- Geographic location of physician site (number and proportion)
- Specialty or area of primary practice (e.g. GPs, cardiologists, endocrinologists (or other diabetes and obesity specialists), etc.) (number and proportion)
- Practice type (e.g. community hospital, academic/medical centre, office based, etc.) (number and proportion)
- Number of physicians who practice at site (mean, standard deviation, median, first and third quartiles and range)
- Patient volume (i.e. number of patients and estimated number of patients using Victoza[®] or Saxenda[®]) (mean, standard deviation, median, first and third quartiles and range)

Patient demographics, medical history, and other characteristics:

Descriptive statistics will be provided for the following variables:

- Age (mean and standard deviation; number and proportion for age categories)
- Sex (number and proportion)

Protocol		Date:	23 November 2015	Novo Nordisk
Study ID: NN8022-4241		Version:	5.0	
UTN: U1111-1185-3661		Status:	Final	
EU PAS No.:	CONFIDENTIAL	Page:	30 of 53	

Drug utilisation:

Descriptive statistics will be provided for the following variables:

Saxenda® or Victoza® patients:

- Brand name (number and proportion)
- Indication prescribed at treatment initiation (number and proportion)
- Target dose prescribed at treatment initiation (number and proportion for target dose categories: 3.0 mg/day (for Saxenda® patients) and 1.2 mg/day, 1.8 mg/day or 3.0 mg/day (for Victoza® patients)

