8.8.1 Monitoring procedures

During the site initiation visit, the monitor will provide training on the conduct of the study to the physician, and all site staff involved in the study. To ensure the integrity of the data, sites will be monitored by a trained monitor. A risk based monitoring approach will be conducted during the study involving remote data monitoring and ad hoc on site monitoring that will be performed to examine compliance with the protocol and adherence to the data collection procedures, to assess the accuracy and completeness of submitted data, and to verify that records and documents are being properly maintained for the duration of the study. The monitor will perform source data verification by review of original patient records. The physician will allow the monitor to have direct access to appropriate parts of patients' medical records relating to their participation in this study, for the purpose of verifying the data submitted by the site.

The monitor will close out each site after the last patient's data collection is completed, all data have been entered in the CRF and all outstanding monitoring issues have been resolved or addressed.

Representatives of Novo Nordisk and Competent Authorities must be permitted to audit/inspect all study-related documents and other materials at the site, including the Investigator Site File, the completed CRFs and the patients' original medical records. Audits/inspections may be conducted at any time during or after the study to ensure the validity and integrity of the study data.

Protocol		Date:	23 November 2015	Novo Nordisk
Study ID: NN8022-4241		Version:	5.0	
UTN: U1111-1185-3661		Status:	Final	
EU PAS No.:	CONFIDENTIAL	Page:	34 of 53	

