Some limitations with regard to data completeness may occur in this study, mainly related to the information captured in the patients' medical records. Measures to ensure the completion of the CRF is conducted in a systematic, professional, and unbiased manner include:

- CRF completion guidelines will provide consistent instructions on completion of the CRF.
- All individuals performing data abstraction from medical records will be trained on appropriate data abstraction techniques in order to minimize possible discrepancies between interpretation of the information recorded by the prescriber in the medical records and the individual performing the review and abstraction of the data.
- Missing data will be followed up on during remote monitoring contacts.

Protocol		Date:	23 November 2015	Novo Nordisk
Study ID: NN8022-4241		Version:	5.0	
UTN: U1111-1185-3661		Status:	Final	
EU PAS No.:	CONFIDENTIAL	Page:	36 of 53	

It is important to capture information on drug use from the start to end of treatment in order to fully assess drug utilisation. However, given the journey of patients with obesity or diabetes - these patients may be treated by several different specialist physicians - complete information over the 24 months of retrospective follow up may not be accessible by the site. For example, for patients whose treatment was initiated in settings other than the study site, there may be a lack of data on treatment initiation (e.g., brand name, start date, prescribed indication and target dose), which are required to fully evaluate drug utilisation. This is a potential limitation inherent of retrospective study designs. In this DUS, every effort will be made - as far as is possible - to obtain data from all relevant healthcare practices in order to capture the journey of patients as fully as possible.

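### Conformity with the Victoza label can be judged only from recorded indication and dose, because evidence of type 2 diabetes is abstracted for Saxenda patients only

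*Protocol*

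**What the plan says.** On analysis, section 8.7.2 of the protocol states: "The main analysis will be to estimate the proportion of prescriptions outside label among" Saxenda or Victoza patients. It adds that the characteristics of patients prescribed either brand "according to the respective approved SmPCs will also be evaluated".

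On classification, section 7.3 counts a Victoza patient under the first secondary objective on either of two criteria: "Dose information of 3.0 mg per day, or" a weight-management indication. The outside-label lists in sections 8.3 and 8.7.2 use the same two categories for Victoza.

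On entry, section 8.2 says that "patients will be identified based on the prescription rather than on a specific diagnosis". Section 6 gives the Victoza label as adults with T2DM, at 1.2 mg and 1.8 mg.

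On data, sections 3.6 and 8.3 place comorbidities under the variables for Saxenda patients only. These include T2DM shown by diagnosis, glucose-lowering therapy, HbA1c, OGTT or FPG. Table 2, for Victoza, has no diagnosis or laboratory row.

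**The concern.** The outside-label proportion and the per-SmPC description are promised for both brands, and the Victoza label depends on having T2DM. For Saxenda, the protocol does not rely on what the prescriber wrote as the reason. It checks BMI and comorbidities, and gives an unmeasured BMI its own outside-label category. For Victoza, the recorded indication is the only evidence on the labelled disease.

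Section 6 names inadvertent use of either product for the other's indication as a reason for the study. If the Victoza indication is blank or wrong, nothing else in the database can reveal that the patient has no diabetes. An analysis plan cannot restore a variable that was never abstracted, so the point has to be settled on the CRF.

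**Working it through.** The protocol gives no sample-size derivation and no expected rates for this topic, so there is no figure to reproduce. The check is one of logic, followed by an illustration of size.

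**1. Evidence available for each brand (sections 3.6, 8.2.6 and 8.3)**

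| Evidence | Saxenda | Victoza |
|---|---|---|
| Recorded indication, target dose | yes | yes |
| Later dose or escalation | yes | yes |
| Weight, height, BMI | yes | no |
| T2DM by diagnosis, therapy or laboratory value | yes | no |

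**2. A patient without diabetes taking Victoza 1.8 mg.** The dose criterion is not met, so everything depends on the indication field.

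- Recorded as weight management: counted, whatever the dose.
- Correctly recorded as some other reason: in neither category, but visible in the table of indications planned in section 8.7.2.
- Missing: in neither category, and no other Victoza variable helps.
- Wrongly recorded as T2DM: in neither category, apparently on label, and possibly placed in the per-SmPC group.

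The gap is the last two cases.

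**3. Size (illustration; both rates are assumptions).** Let p be the share of the 150 full-study Victoza patients (section 8.2.1) who have no T2DM and take less than 3.0 mg/day. Let m be the share of those with a missing or wrong indication. Unidentified patients = 150 × p × m.

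- p = 5%, m = 10%: 150 × 0.05 × 0.10 = 0.75 patients (0.5%)
- p = 10%, m = 20%: 150 × 0.10 × 0.20 = 3 patients (2.0%)
- p = 20%, m = 30%: 150 × 0.20 × 0.30 = 9 patients (6.0%)

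**4. Direction.** If these patients stay in the denominator, the outside-label proportion is too low by the percentages above. Section 8.7, however, summarises categorical participant characteristics on non-missing data. Suppose that convention were carried over, so that d patients with a missing indication are dropped, u of them truly outside label, while c are counted. The estimate is c/(150 − d) against a true (c + u)/150, taking the indication as correct in everyone retained. It is too low only if u/d exceeds c/(150 − d), that is, if outside-label use is commoner among those dropped than among those kept. The direction is therefore not certain for missing indications. For wrongly recorded ones, the count can only fall short.

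**The case against.** The strongest reply is that the study asks about Victoza used for weight management, and that the two criteria are applied consistently to that question. This stands for the section 7.3 endpoint. A reader might infer that the endpoint itself is defective or would be repaired by T2DM data. The documents do not support that: having T2DM does not exclude weight-management intent, and lacking it does not prove it. A reader might also blame the missing variable alone. The two-category definition in section 8.3 contributes equally, and T2DM data would make these patients visible without moving them into the endpoint.

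The reply does not cover section 8.7.2, which extends the analysis to outside-label and per-SmPC use of both brands.

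Second, missing indications are disclosed and mitigated. Section 8.9 warns, with treatment begun elsewhere as its example, that "there may be a lack of data on treatment initiation (e.g., brand name, start date, prescribed indication and target dose". It promises every effort "to obtain data from all relevant healthcare practices". Some of these patients may also fail the initiation criterion in section 8.2.2. Section 8.8.1 adds: "The monitor will perform source data verification by review of original patient records". These steps shrink the gap without closing it. An indication that nobody recorded cannot be retrieved, and source verification compares the CRF with the chart, not the charted indication with diabetes status. Section 8.1.1 allows refinements after the pilot, but the pilot examines only variables used for the specified endpoints, so nothing planned would prompt this one.

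Third, the SAP could define the per-SmPC group as requiring a recorded T2DM indication, and could count unrecorded indications. Both are fair points; only wrongly recorded indications would then contaminate that group. The protocol gives no rate of wrong recording and does not suggest that it is common.

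**Conclusion.** The point holds as a limited gap in data collection. For Victoza, conformity with the labelled disease rests on the recorded indication, and the protocol collects nothing that could test it. The patients affected are those without diabetes, below 3.0 mg/day, whose indication is missing or wrong.

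The number is unknown and probably small. The range of 0.5% to 6.0% rests wholly on assumed rates, and the direction of bias depends on how missing indications are handled. A reader might conclude that the outside-label proportion is materially understated; the documents give no basis for that. This is a worthwhile, low-cost improvement to the section 8.7.2 analysis, not a fault in the weight-management endpoint.

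**What to change.** Add T2DM status to the Victoza CRF and to Table 2, preferably before the pilot and at the latest before the full study.

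- **Definition.** Use a recorded diagnosis, or HbA1c, FPG or OGTT in the T2DM range of section 8.3. Treat other glucose-lowering therapy as supporting evidence only, because the section 8.3 therapy rule identifies dysglycaemia, which includes prediabetes. Exclude liraglutide itself: the PASS information table gives it an A10 code, so every Victoza patient would otherwise qualify.
- **Reporting.** Leave the section 7.3 endpoint as it is. In the section 8.7.2 analysis, show Victoza patients with no evidence of T2DM as a separate category of possible outside-label use, cross-tabulated with recorded indication. Describe the per-SmPC Victoza group with and without them.

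The cost is a few fields from a chart that is already being abstracted, plus one table. Some patients whose diabetes is documented elsewhere will fall wrongly into the new category. It must therefore be labelled as possible, and must not be read as proven weight-management intent.

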8.1 Study design

8.1.1 Type of study

This DUS is a non-interventional, multi-centre Post Authorisation Safety Study (PASS) to investigate the use of Saxenda[®] and Victoza[®] in clinical practice in patients who have initiated treatment in the Saxenda[®] postmarketing period. The DUS involves retrospective review of patients' medical records in two selected European Union (EU) countries 24 months after launch of Saxenda[®] in each of the countries. Physician sampling will be built using several tools, including intelligence databases, e.g., IMS LifeLinkTM, in order to obtain a representative sample of Saxenda[®]/Victoza[®] prescriptions according to physician specialty and geography. This data source will be complementary to the full study and will be obtained on a quarterly basis, during the study period. It will provide, on a national level for the two targeted countries, the distribution of sites and prescribers' specialty. It will not identify individual prescribers, but rather guide the site selection for the study performed by Therefore, IMS LifeLinkTM will be used a priori to refine the sampling strategy (using regional and specialty distribution of prescribers), and a posteriori to assess the representativeness of prescribers and patients, for both the pilot and full study.

A case report form (CRF), including all the desired data elements, will be available to the selected sites; one CRF is to be completed per patient prescribed Saxenda® or Victoza®. The CRF may be completed by a trained healthcare professional at the site, or by a trained external medical record abstractor. The data will be entered pseudonymised into the CRFs.

A pilot study, to be embedded in the full study, will be conducted 6 months after launch of Saxenda[®] in each of the two countries, i.e., prior to the full DUS. The objective of the pilot study is to evaluate the feasibility of the full DUS. The feasibility will be evaluated on three main parameters:

- 1. Possibility of identifying physicians prescribing Saxenda®/Victoza® and participating sites
- 2. Possibility of identifying patients treated with Saxenda® or Victoza®

Protocol		Date:	23 November 2015	Novo Nordisk
Study ID: NN8022-4241		Version:	5.0	
UTN: U1111-1185-3661		Status:	Final	
EU PAS No.:	CONFIDENTIAL	Page:	19 of 53	

3. Availability and quality of the variables used to determine the specified endpoints (see section 7.3)

Based on the data obtained in the pilot study, full study refinements may be necessary before the full retrospective medical record review is implemented in the two countries.

The index date, defined as the start date of data abstraction, will be 6 months after the launch of Saxenda[®] for the pilot, and 24 months after launch for the full study (see Figure 1 for an overview of the study design). The launch date may be different in the two countries. The data will be collected only after informed consent has been obtained from the patients. All study prescribers within a country will be assigned the same index date and will not be contacted prior to it. Initiation of prescriber-specific activities for selection of patient records meeting study selection criteria will commence on or following the index date. Data on drug utilisation will be censored on the index date. This approach will ensure that study procedures do not influence prescribing practices.

 Protocol
 Date:
 23 November 2015
 Novo Nordisk

 Study ID: NN8022-4241
 Version:
 5.0

 UTN: U1111-1185-3661
 Status:
 Final

Page:

20 of 53

CONFIDENTIAL

[figure not shown]

Figure 1 - DUS overview

EU PAS No .:

Notes: The index date (start date of data abstraction) for the pilot study will be 6 months following the launch of Saxenda[®] in the participating countries; data will be collected on patients from their start date of Saxenda[®]/Victoza[®] until the index date for the pilot study. The index date for the full study will be 24 months after the launch of Saxenda[®]; data will be collected on patients from their start date of Saxenda[®]/Victoza[®] until the index date for the full study. ICF: Informed Consent Form; M: month

8.1.2 Rationale for study design

The study design is in accordance with the study objectives. Being retrospective in design, this study will involve no intervention, and so will not impact usual medical care or affect the treatment of patients. Thus, the study will reflect real-world medical practice without the potential for prescriber response bias which may occur in prospective studies (i.e., the Hawthorne Effect [3]). The full study will not use the same sites and patients as the pilot study in order to account for potential bias, e.g., prescriber response bias, which may be associated with awareness of study objectives following the pilot study. Furthermore, data collection will be initiated following the study-defined abstraction index date. Initiation of selection of patient records meeting study selection criteria will commence on or following this date. Data on drug utilisation will be censored from then and not considered in the analyses. This approach will ensure that study procedures do not influence prescribing practices.

8.1.3 Treatment of patients

Patients will be treated with commercially available Saxenda® or Victoza® according to routine clinical practice at the discretion of the treating physician. Saxenda® and Victoza® both contain the

Protocol		Date:	23 November 2015	Novo Nordisk
Study ID: NN8022-4241		Version:	5.0	
UTN: U1111-1185-3661		Status:	Final	
FILPAS No.	CONFIDENTIAL	Page.	21 of 53	

active substance liraglutide - a long-acting GLP-1 analogue, and are both administered subcutaneously by injection. The approved posology for Saxenda[®] is a starting dose of 0.6 mg daily, which should be increased to 3.0 mg daily in increments of 0.6 mg with at least one week intervals to improve gastrointestinal tolerability. For Victoza[®], the approved posology is a starting dose of 0.6 mg daily, which should be increased to 1.2 mg after at least one week; based on glycaemic response, the daily dose can be increased from 1.2 mg to 1.8 mg after at least one week.

8.2 Setting

Since the purpose of this study is to investigate real-world, in-market utilisation of liraglutide, patients will be identified based on the prescription rather than on a specific diagnosis. The study will target first-time patients of Saxenda® or Victoza® by identifying a representative sample of physicians who treat diabetic or obese patients for whom Saxenda® or Victoza® can be prescribed. These include general practitioners (GPs), endocrinologists and cardiologists (or other diabetes and obesity specialists) from a variety of settings (e.g., office-based vs. hospital-based, urban vs. rural). Once prescribers of Saxenda® or Victoza® are identified, these will be oversampled to ensure adequate numbers of prescribers (and therefore patients).

